### 6.2.3 Multiple target lesions/vessels treatment

Subjects requiring multi-vessel PCI may be enrolled in this trial. There is no limit on the number of target lesions per epicardial vessel and target vessels per patient in this study. All target lesions and vessels must satisfy all inclusion and exclusion criteria.

*This confidential document is the property of Abbott and shall not be reproduced, distributed, disclosed or used without the express written consent of Abbott*

## Clinical Investigation Plan

### 6.2.4 Non-target lesion/vessel treatment

Non-target lesion/vessel treatment (i.e., lesion/vessel that does not meet the inclusion/exclusion criteria) are not allowed prior to or during the study-required procedure. They may be treated either after the study-required procedure is completed within the same PCI procedure or as a staged procedure. In either case, the study participation will end at the completion of the study-required procedure (during the index procedure).

### 6.2.5 Staged procedure considerations

All aspects of the study protocol must occur during one procedure, which is considered the study index procedure. This may be a planned staged procedure based on a diagnostic catheterization (pre-or post-consent). Subject participation begins at the index procedure upon study device insertion in enrolled subjects. The enrollment is based on subjects satisfying all eligibility criteria and had a successful pre-PCI physiological indices measurement and OCT imaging conducted on the qualified lesion(s)/vessel(s). Subject participation ends at the conclusion of the study index procedure with or without PCI performed. There will be no data collection from any additional staged procedure as subject participation ends at the conclusion of the study index procedure and the subject cannot be re-enrolled in the study.

[figure not shown]
### 6.2.6 Bifurcation lesions consideration

Bifurcation lesions consideration is shown in **Figure 4**.

- **Scenario 1:** For the main branch lesion with a side branch that has a minimal disease which is defined as <40% diameter stenosis by visual estimate), the main branch lesion can be enrolled as the target lesion. Treatment of the side branch is optional and outside of the study protocol.
- **Scenarios 2 and 3:** If the side branch vessel has significant ostial disease with a planned single (**Scenario 2**) or two-stent (**Scenario 3**) strategy, only the main vessel can be enrolled into the study, following the FUSION workflow in the main branch. For two-stent strategy, this will count as one lesion and physiology measurement and OCT imaging are not required in the side branch. Treatment of the side branch will be outside of the study protocol.
- **Scenario 4:** For the main branch and side branch lesions that are both to be considered as target lesions, these two lesions need to be distant from each other (i.e., side branch lesion is not ostial) treated independently and both branches are of adequate size to undergo physiology and OCT measurements. In that setting, the main and the side branch are considered separate target vessels and all physiology and OCT. The measurements of both physiology and OCT must be done in the respective target vessel separately. i.e., in the side branch for the side branch lesion assessment. Of note, while assessing side branch lesions, upstream lesions in the main branch must also be imaged.

## Clinical Investigation Plan

Figure 4: Bifurcation Lesions Consideration

*This confidential document is the property of Abbott and shall not be reproduced, distributed, disclosed or used without the express written consent of Abbott*

## Clinical Investigation Plan

### 6.3 Post-PCI (In-hospital)

The timing and method of vascular sheath removal, as well as timing of ambulation, use of post-procedural medications and discharge is per standard of care. Study participation ends when the subject leaves the catheterization laboratory.

### 6.4 Follow-up Assessments

No follow-up will be required in this study.

### 6.5 Additional Information on Required Assessments

#### Physical Examination

Physical examination will be completed and recorded at baseline. Any clinically significant findings during the physical examination should be reviewed by the investigator. Any clinically significant findings during the baseline physical examination should be reported in the subject medical history. Any clinically significant findings during physical examinations post-device insertion should be reported as adverse events. Physical examinations should be performed per the standard of care and may be completed by any qualified medical personnel.

## Clinical Investigation Plan

### 6.5.1 Schedule of Events

| CIP Activity                                 | Enrollment | Baseline
(within 30 days otherwise stated in the CIP) | Procedure        |
|--|------------|--|------------------|
| Informed Consent Process              | X          |  |                  |
| Demographics and Medical History      |            | X  |                  |
| Physical Exam                         |            | X  |                  |
| Pregnancy Test            |            | X  |                  |
| LVEF                                  |            | X  |                  |
| NYHA Assessment                       |            | (X)  |                  |
| 12 Lead ECG                           |            | X  |                  |
| Serum Creatinine                      |            | X  |                  |
| Hematocrit                            |            | X  |                  |
| Hemoglobin                            |            | X  |                  |
| Pre-PCI Angiography                   |            | X  |                  |
| Pre-PCI Physiological Indices         |            |  | X                |
| Pre-PCI OCT                           |            |  | X                |
| Pre-PCI Angiographic Co-registration  |            |  | X                |
| PCI                                   |            |  | (X)              |
| Post-PCI OCT                          |            |  | (X)  |
| Post-PCI Angiographic Co-registration |            |  | (X)  |
| Post-PCI Physiological Indices        |            |  | (X)  |
| Post-PCI Angiography                  |            |  | (X)  |
| Cardiac Medications                   |            | X  |                  |
| Adverse Event                         |            |  | X                |

For women of childbearing potential

Optional

## Clinical Investigation Plan

### 6.6 Physiology and OCT Core Laboratories

This clinical investigation will utilize an independent core laboratory for the assessment and evaluation of all pre-and post-PCI OCT pullback images and corresponding pressure recordings required during the clinical investigation period.

All clinical investigation-required pre-and post-PCI OCT pullback images and corresponding pressure recordings should be submitted to the core laboratories by uploading the assessments directly to the core laboratory's database. The core laboratory will review and provide quality check of all pullback images and pressure tracings.

The core laboratory will review co-registered angiography and OCT pullbacks, and exclude cases with spastic artery, myocardial bridge and accordion effect. After successful auto-calibration of OCT pullback, the core laboratory will exclude cases with low image quality caused by significant blood in lumen or catheter purge issue as well as cases that present with OCT artifact. The core laboratory will reject pullback with the presence of ruptured plaques, hematoma, thrombus or old stent.

Pressure tracings will also be reviewed for pressure drift and significant artifacts per the core laboratory's standard operational procedure, and reasons of rejection for each unacceptable pressure tracing will be documented by the core laboratory.

All the remaining acceptable OCT pullback images and pressure tracings will be used for endpoint analysis. VFR computed using Abbott validated software will be validated against the core lab reported FFR.

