## 6.2 PCI Procedure

The following is a description of the image acquisition and treatment steps to be used during the index procedure. The pre-PCI procedures should be conducted in the following order: Pd/Pa and RFR snapshot measurement, FFR measurement, dedicated period for resolution of hyperemia, RFR pullback measurement, drift check, and OCT imaging procedure. The optional post-PCI step should include final OCT imaging procedure, followed by physiological measurements (refer to the flowchart in **Figure 2**). Post-PCI study data collection step is optional but strongly recommended if PCI is performed.

All OCT data and physiological indices measurements will be stored digitally for subsequent analysis and these images must be sent to the Core Laboratory for quality check.

Any vessel preparation (if necessary) with balloon dilation or atherectomy should be performed only after pre-PCI physiological indices measurement and OCT have been performed.

If applicable, PCI will be performed according to local standard practice. PCI information will be collected on the appropriate eCRF. For each treated lesion, the guiding catheter size, the total number of stents used, and the relevant stent information (diameter and length) must be recorded on the appropriate eCRF. Any vessel preparation step including, pre-dilation, post-dilation, or atherectomy device use must also be recorded. If the subject undergoes atherectomy during PCI, post-PCI OCT and physiological steps are not needed and that is the end of the protocol for the subject.

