### 6.2.2 OCT procedures

The preparation and use of the OCT catheter will be according to its respective IFU. For all indicated vessels, if less than 10 minutes have passed since the last dose of IC nitroglycerine, no extra dose is needed. If more than 10 minutes have passed since the last dose of IC nitroglycerine, at least 100 µg IC nitroglycerin should be re-administered before OCT pullbacks. The proximal and distal reference segments are initially identified by angiography. The proximal and distal reference diameters should be recorded on the eCRF. OCT Imaging must be performed using the pullback device at 75 mm pullback (survey mode), 5 frames per mm over 2.1 seconds. The OCT catheter should be placed at the location where the imaging lens is at the same location as the PressureWire sensor and would reach the guide catheter at the end of the imaging run as well as at least 10 mm distal to the distal end of the lesion, with the aim of imaging as much of the coronary artery as possible. All significant lesions in a vessel need to be within a single OCT pullback. OCT pullback image will be qualified as long as all disease segment was captured. The lens position should be captured via cine documentation prior to each pullback. For standard pullback, the recommended contrast injection volume is 14 ml at an injection rate of 4 mL/s in the left coronary artery and 12 mL at an injection rate of 3 mL/s in the right coronary artery. Cine angiography with contrast opacification of the coronary artery in the desired angiographic co-registration view(s) must be performed during the pre- and (optional) post-PCI OCT pullback without panning. Contrast volume and method are collected on the eCRF.

For cases with PCI, the post-PCI study data collection step is optional. If a post-PCI study data collection was performed, both intermediate and final OCT pullbacks should be collected after OCT-guided stent optimization was done, and the post-PCI physiological assessment must be performed after the final OCT run. Pre-PCI, (optional) intermediate post-PCI, and (optional) final post-PCI OCT pullback images need to be uploaded to the OCT Core Laboratory via BioClinica website.

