### **8.1 Analysis Populations**

The primary analysis population will include all subjects who have signed informed consent, met all inclusion and exclusion criteria, and have acceptable OCT pullbacks and pressure tracings for computing both the VFR and FFR indices

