2.3.2.2.2 Analysis Method

The overall specificity will be estimated using the 2×2 contingency table comparing VFR and FFR measurements. Specificity is defined as the proportion of VFR negative lesions in the group of FFR negative lesions (Šimundić, 2009 Jan), which can be expressed in the following way:

$$Specificity = \frac{TN}{TN + FP}$$

Where TN denotes the number of True Negatives (both VFR and FFR negatives) and FP denotes the number of False Positives (VFR positive but FFR negative).

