2.8 Subgroups for Analysis

2.9 Handling of Missing Data

Every effort will be taken to obtain complete data for all subjects. Any subject without a pair of qualified FFR and VFR measurements will be excluded from analysis.

Statistical Analysis Plan

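### The readable plan does not say that the co-primary 2x2 table uses pre-PCI pairs only, while CIP 6.6 sends all acceptable pre- and post-PCI data to endpoint analysis

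*Protocol*

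**What the plan says.** CIP 6.6 gives the core laboratory the "assessment and evaluation of all pre-and post-PCI OCT pullback images and corresponding pressure recordings". It lists the reasons for rejection, among them "The core laboratory will reject pullback with the presence of ruptured plaques, hematoma, thrombus or old stent", and ends: "All the remaining acceptable OCT pullback images and pressure tracings will be used for endpoint analysis". The sentence after that says VFR will be validated against the FFR reported by the core laboratory, which is the co-primary comparison.

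Post-PCI data are a real data stream. CIP 6.2 says: "Post-PCI study data collection step is optional but strongly recommended if PCI is performed". Where the step is done, CIP 6.2.2 says that "the post-PCI physiological assessment must be performed after the final OCT run", so a final post-PCI pullback has its own FFR. An intermediate pullback does not.

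The analysis population (CIP 8.1, repeated in SAP 2.1.1) is subjects who meet the eligibility criteria and "have acceptable OCT pullbacks and pressure tracings for computing both the VFR and FFR indices". The endpoints count lesions. SAP 2.3.2.2.2 reads: "Specificity is defined as the proportion of VFR negative lesions in the group of FFR negative lesions". SAP 2.9 adds: "Any subject without a pair of qualified FFR and VFR measurements will be excluded from analysis". None of these says which pair is meant when a vessel has two.

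**The concern.** Read literally, CIP 6.6 lets a vessel that was stented in the study procedure contribute twice: once before PCI and once after. The stent rejection reason is aimed at stents already present, so the new stent is not a stated ground for leaving the second pair out.

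The stated use of VFR is to diagnose the functional significance of coronary stenoses, with procedural planning as a further use (CIP 2.2.2). If FFR after stenting is mostly above 0.80 and VFR does not read low there, the added pairs are mostly easy true negatives. Specificity then rises with no better performance on untreated lesions. If VFR reads low after stenting, specificity falls. The few post-PCI pairs with FFR at or below 0.80 could lower sensitivity.

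In each case the co-primary result would depend on how many sites chose to do an optional step. Two entries from one vessel are also correlated, and the only readable allowance for that is an optional model in SAP 2.13.

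**Working it through.** **Which text sets the time point**

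| Text | Time point named? |
|---|---|
| CIP 6.6, data sent to endpoint analysis | Pre- and post-PCI data covered; none singled out |
| CIP 8.1 and SAP 2.1.1, population | No |
| CIP 8.2.1 and SAP 2.3.1-2.3.2, 2x2 table and definitions | No |
| CIP 8.4 and SAP 2.6, timing | No |
| SAP 2.9, missing data | No; asks for one qualified pair |
| CIP 6.2.5, enrollment | Pre-PCI |
| CIP 5.3.4, imaging exclusions | Pre-PCI OCT |
| CIP 3.2.2 and SAP 1.6, balancing of FFR | Baseline |

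The last three rows point to pre-PCI pairs, but they govern enrollment, eligibility and monitoring. They do not define the table.

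**Size, as an illustration**

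The plan's own figure of 310 subjects cannot be reproduced, because the goals, assumed rates, prevalence and power are not readable. It is not disputed here.

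From the documents: 310 subjects; one-sided hypotheses (SAP 2.3.2.1.1 and 2.3.2.2.1) tested at 0.025 (SAP 2.7). Assumed: 40% of pre-PCI vessels FFR-positive with one vessel per subject, giving 310 × 0.60 = 186 negatives and 124 positives; goal 0.75; exact binomial test; independent pairs; true pre-PCI specificity equal to the goal.

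With *m* post-PCI negatives of specificity *s*:

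- Pooled specificity = (186 × 0.75 + *m* × *s*) / (186 + *m*). For *m* = 20 and *s* = 0.90: (139.5 + 18) / 206 = 0.765.
- The test passes if correct negatives reach *c*, the smallest count whose upper tail at 0.75 is at most 0.025.
- The chance of passing is the upper tail at *c* of the sum of Bin(186, 0.75) and Bin(*m*, *s*).

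| *m* | n | *c* | s=0.60 | 0.70 | 0.75 | 0.85 | 0.90 | 0.95 |
|---|---|---|---|---|---|---|---|---|
| 0 | 186 | 152 | 1.9% | 1.9% | 1.9% | 1.9% | 1.9% | 1.9% |
| 10 | 196 | 160 | 0.9% | 1.4% | 1.7% | 2.5% | 3.0% | 3.6% |
| 20 | 206 | 167 | 0.7% | 1.7% | 2.4% | 4.8% | 6.6% | 8.9% |
| 40 | 226 | 183 | 0.2% | 1.0% | 2.1% | 7.5% | 12.9% | 20.6% |

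The 0.75 column shows test discreteness alone, so changes of half a percentage point mean nothing.

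Varying the assumptions, with post-PCI specificity 0.90-0.95 and 0, 10, 20 and 40 post-PCI negatives:

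- 155 to 217 pre-PCI negatives, goal 0.75: 1.6-2.1%, 3.2-5.1%, 4.7-9.1%, 12-22%.
- Goal 0.70, 186 negatives: 2.3%, 3.5-4.1%, 7.1-9.3%, 21-31%.
- Goal 0.80, 186 negatives: 2.2%, 3.6-4.4%, 3.8-5.5%, 8.9-15.5%.

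**Sensitivity.** Assume 124 pre-PCI positives at a true 0.85, plus *k* post-PCI positives detected at 30-50%. Pooled sensitivity is (124 × 0.85 + *k* × rate) / (124 + *k*): 0.83-0.84 for *k* = 5 and 0.81-0.82 for *k* = 10. Against a goal of 0.75, the chance of passing falls from 77% to 55-64% and to 32-50%.

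**The case against.** The strongest reply is that pre-PCI is the natural reading. CIP 6.6 is a data-flow section; it says endpoint analysis, not co-primary analysis, and it twice speaks of required recordings, whereas post-PCI recordings are optional. Membership of the analysis set comes from CIP 8.1, which requires the eligibility criteria to be met. Those concern lesions of 40-90% visual stenosis (CIP 5.3.2), unprepared before pre-PCI measurement (CIP 5.3.4), and CIP 6.2.3 applies all criteria to every target lesion and vessel. A freshly stented segment does not fit that description well.

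Much of this stands as evidence of intent, and it is why the point is an ambiguity. It does not settle the matter. The sentence of CIP 6.6 that speaks of required recordings itself names post-PCI pullbacks. The eligibility text says which lesions qualify, not which measurement of a qualifying lesion is counted.

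Second, a limit may be hidden. The CIP sensitivity and specificity hypotheses, CIP 8.3, and SAP 2.4, 2.8 and 2.10 cannot be read in whole or part, and nothing lost to redaction counts against the plan. This stands. If the limit is there, CIP 6.6 is only out of line with it.

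Third, pooling might be deliberate, since VFR is also meant for procedural planning. In that case passing would not be wrong in the sense used above, but the plan should say so and justify it.

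The revision history does not decide the question. Version B added a pre- versus post-PCI subgroup; version F changed the sample-size assumptions, including one about post-PCI FFR, and made post-PCI collection optional. These entries describe changes, can be read either way, and do not define the current table.

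A reader might infer that the trial will pool post-stent pairs and so inflate specificity. The documents support neither half: they leave the set open, and the direction depends on how VFR behaves after stenting, for which they give no figure.

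**Conclusion.** The point holds as an ambiguity in the co-primary data set. One sentence in CIP 6.6 admits post-PCI pairs; no readable co-primary text excludes them; other wording leans towards pre-PCI; and redacted text may already resolve it.

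The illustration shows why it is worth settling. At an assumed goal of 0.75, the chance of wrongly passing specificity rises from 1.9% to 6.6-8.9% with 20 post-PCI negatives and 13-21% with 40, provided VFR has specificity 0.90-0.95 after stenting. At 0.75 there is no material change, and at 0.60-0.70 the chance falls to 0.2-1.7% over 10 to 40 post-PCI negatives. Only the 0.025 level, the one-sided form and the 310 come from the documents.

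A reader might go on to infer a trial-level false-success rate by multiplying these figures by a fixed chance of passing sensitivity. That is not supported. Post-PCI positives could cut that chance, as shown above, so the two effects partly offset. No trial-level figure is claimed.

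**What to change.** - CIP 8.2.1 and SAP 2.3.2: add *Both co-primary endpoints use pre-PCI VFR-FFR pairs only.*
- CIP 6.6: reword the closing rule so that acceptable pre-PCI pullbacks and tracings go to the co-primary analysis and acceptable final post-PCI pairs are analyzed separately.
- SAP: report final post-PCI pairs in their own descriptive table, outside the success criteria.

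If redacted text already sets the limit, only CIP 6.6 needs aligning. The change should be made before the analysis group is unblinded to VFR, so that the choice cannot be informed by results.

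The cost is one sentence in each of three places and one table, with no new procedure or data. The small downside is that post-PCI pairs no longer add to co-primary precision. Because CIP 8.3 is unreadable, the sponsor should confirm that the 310 does not count them.

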## 7.0 ADVERSE EVENTS

To comply with worldwide standards and guidelines on clinical investigation adverse event reporting, the Sponsor has adopted uniform and worldwide applicable standard definitions and reporting timelines to be used and adhered to by the investigators.

### 7.1 Definition

#### 7.1.1 Adverse Event

An adverse event (AE) is any untoward medical occurrence, unintended disease or injury, or untoward clinical signs (including abnormal laboratory findings) in subjects, users or other persons, whether or not related to the medical device under investigation.

**Note 1:** This definition includes events related to the medical device under investigation or the comparator.

**Note 2:** This definition includes events related to the procedures involved.

**Note 3:** For users or other persons, this definition is restricted to events related to medical devices under investigation.

*This confidential document is the property of Abbott and shall not be reproduced, distributed, disclosed or used without the express written consent of Abbott*

## Clinical Investigation Plan

### 7.1.2 Serious Adverse Event

If the AE meets any of the criteria below, it is regarded as a serious adverse event (SAE).

- a) Led to a death,
- b) Led to a serious deterioration in health of the subject, that either resulted in
  1. a life-threatening illness or injury, or
  2. a permanent impairment of a body structure or a body function, or
  3. in-patient hospitalization or prolongation of existing hospitalization, or
  4. medical or surgical intervention to prevent life threatening illness or injury or permanent impairment to a body structure or a body function.
  5. chronic disease
- c) Led to fetal distress, fetal death or a congenital abnormality or birth defect.

**Note:** A planned hospitalization for pre-existing condition, or a procedure required by the CIP, without a serious deterioration in health, is not considered to be an SAE.

